5.2 Exclusion Criteria

1. Platelet count greater or equal to 100,000/ μ L
2. Severe active infection indicated by sepsis (requirement for pressors with or without positive blood cultures)
3. Clinical evidence of enteric infection with *E. coli* 0157 or related organism
4. Anti-phospholipid syndrome
5. Diagnosis of DIC
6. Pregnancy or breast-feeding
7. Haematopoietic stem cell or bone marrow transplantation-associated thrombotic microangiopathy
8. Known congenital TTP
9. Active bleeding or high risk of bleeding
10. Uncontrolled arterial hypertension
11. Known chronic treatment with anticoagulant treatment that can not be stopped safely, including but not limited to:
 - vitamin K antagonists
 - heparin or LMWH
 - non-acetyl salicylic acid non-steroidal anti-inflammatory molecules
12. Severe or life threatening clinical condition other than TTP that would impair participation in the trial

13. Subjects with malignancies resulting in a life expectation of less than 3 months
14. Subjects with known or suspected bone marrow carcinosis
15. Subjects who cannot comply with study protocol requirements and procedures.
16. Known hypersensitivity to the active substance or to excipients of the study drug
17. Severe liver impairment, corresponding to grade 3 toxicity defined by the CTCAE scale. For the key liver parameters, this is defined as follows:
 - bilirubin > 3 x ULN (need to differentiate isolated increase in indirect bilirubin due to haemolysis, this is not an exclusion parameter but disease related)
 - ALT/AST > 5 x ULN
 - AP > 5 x ULN
 - gamma glutamyl transpeptidase (GGT) > 5 x ULN
18. Severe chronic renal impairment, as defined by GFR < 30 mL/min

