- Urine pregnancy test for female subjects (Human chorionic gonadotropin (hCG) only) (local laboratory)
- Blood typing (ABO, Rh) and direct antiglobulin test (DAT) (local laboratory)
- Blood sampling for chemistry will include the following: glucose, bilirubin (total), AP, AST, ALT, LDH, C-reactive protein (CRP), hCG (for women, only if urine pregnancy test not feasible or inconclusive), haptoglobin, rheumatoid factor, antinucleic acid, iron, ferritin, transferrin, creatinine, urea (blood urea nitrogen (BUN)), uric acid, protein, albumin, sodium (Na), potassium (K), calcium (Ca), magnesium (Mg) and chloride (Cl) (local laboratory)
- Blood sampling for haematology will include the following: haemoglobin, haematocrit, mean corpuscular volume (MCV), mean corpuscular haemoglobin (MCH), mean corpuscular haemoglobin concentration (MCHC), full blood count including red blood cells (RBC), white blood cells (WBC), differential, reticulocytes, optical platelet count and immature platelet fraction (local laboratory). In case optical platelet counts are not available, they can be replaced by measurements based upon impedance. If not available in the local laboratory, immature platelet fraction measurements can be omitted
- Blood sampling for coagulation variables will include: fibrinogen, aPTT, PT, international normalised ratio (INR), vWF:Ag, FVIII chromogene, lupus anticoagulant, anticardiolipin antibodies (antiphospholipid) (local laboratory). In case FVIII chromogene is not available in the local laboratory, it can be replaced by an alternative method (e.g. one stage clotting assay)
- Blood sampling for viral serology (hepatitis B virus (HBV), hepatitis C virus (HCV), HIV subtype-1 and -2 [HIV-1 and HIV-2]) (local laboratory)
- Blood sampling for ADAMTS13 and anti-ADAMTS13 antibody titre (central laboratory).

The following procedures must be performed after randomisation, as baseline assessments (see Table 10):

- Prior and concomitant medication taken during the 30 days prior to the screening examination are to be documented. Concomitant medication from the 30 days prior to screening until follow-up or started during the course of the study will be recorded on the Concomitant Medications page of the CRF. Concomitant medications initiated, stopped, up-titrated or down-titrated for an AE will also be recorded on a specific Concomitant Medications page of the CRF.

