### **6.2.4 Baseline Disease Characteristics**

Baseline disease characteristics presented will be platelets, LDH, ADAMTS13 activity (subdivided into < 5% and ≥ 5%), ADAMTS13 functional inhibitors (categorised as <0.5 BU/mL, ≥0.5 BU/mL and ≤2 BU/mL, >2 BU/mL, >>2 BU/mL), vWF:Ag levels, initial

---

or recurrent episode (where an episode is considered to be recurrent for subjects with one or more occurrences of MedDRA preferred term “THROMBOTIC THROMOCYTOPENIC PURPURA” at latest, the month preceding the month of first dosing within the Medical History data), PE prior to randomisation (Yes/No) and exploratory markers of disease such as cardiac markers (TnT or TnI, BNP or NT-proBNP) and brain damage markers (NSE, S $\beta$ 100) for ITT and PP populations. ADAMTS13 activity will also be summarised separately for subjects having or not having received one PE prior to randomisation.

Baseline disease characteristic data will be listed and summarised using summary statistics for continuous variables (number of subjects [n], mean, standard deviation [SD], median, minimum and maximum) or by way of group frequencies and percentages for categorical variables, as appropriate.

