### *Subgroup analyses*

In addition to the KM estimates, the corresponding Cox proportional hazard regression model with baseline disease characteristics (ADAMTS13 activity  $< 5\%$  versus  $\geq 5\%$ , vWF level (continuous), first episode versus recurrent disease (as described in [Section 6.2.4](#)), presence or absence of RICO suppression of  $< 20\%$  throughout treatment period, one PE prior to randomisation or not) will be used to estimate the hazard ratio (HR) and associated 95% CIs for the HR for ALX-0081 and placebo group. This will be represented by means of Forest plots.

The trial was not sized to test for the presence of treatment by subset interactions. Thus true treatment by subset interactions would likely be missed, unless they are substantial. Conversely, should any particular subset of subjects seem to benefit more or less from therapy than the total population, this would not be taken as evidence of a true treatment by subset interaction, given the likelihood that such an observation could be due to chance alone.

Underlying model assumptions will be investigated for the survival analysis using diagnostic statistics and graphical methods, and if necessary, an alternative analysis technique may be used. Any changes in methodology will be documented in the clinical study report (CSR, to be produced by [REDACTED]), including the rationale for use. The proportional hazards assumption will be assessed by graphical display of the log-log survival distribution function versus the log event time for each treatment group.

In order to accommodate tied time-to-event data, the EXACT option within SAS PROC PHREG shall be used. This method assumes that there is a true but unknown ordering for the tied event times, and that the ties are merely the results of imprecise measurements of time.

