### *Sensitivity analyses with regards to primary (and secondary) efficacy endpoints*

Sensitivity analyses comprise the following aspects:

- 1) For efficacy endpoints (EPs) (primary and secondary), analyses performed on per protocol (PP) populations. Details on major deviations are specified in [Appendix II](#).
- 2) Analysis of treatment effect adjusted for the following covariates:
  - a. ADAMTS13 activity at baseline: < 5% vs.  $\geq$  5%,
  - b. von Willebrand Factor (vWF) level (continuous),
  - c. first episode vs. recurrent disease (as described in [Section 6.2.4](#)),
  - d. Ristocetin Cofactor (RICO) suppression < 20% throughout treatment period: yes vs. no,
  - e. absence/presence of one PE session prior to randomisation.

A Cox proportional hazards model is fit to the data, and in addition to treatment, significant (5% significance level; SL) covariates are retained. This will be represented by means of Forest plots for the covariates found to be significant.

- 3) Analysis of non-confirmed and confirmed platelet response (instead of confirmed platelet response only) for the ITT population: see **Table 2**, with changes to
- 4) **Table 1** indicated in **bold green**.
- 5) Assessment of impact (potential bias) of use of rituximab during daily PE: log rank analysis of primary endpoint with subjects censored at time they start using rituximab for the ITT population. Use of rituximab will be determined by using the Concomitant Medications data (both PE related and not PE related) with ATC code “L01XC” (coded term “RITUXIMAB”).

**Table 2: Censoring/event scenarios (for ITT and PP analysis of non-confirmed and confirmed platelet response; changes to Table 1 indicated in bold green)**

Case	Description	Time at risk/ Time to recovery of platelets (days)	Responder	Censored (No = 0; Yes = 1)
1	No event in 30 days of continuous daily PE a	30	No	1
2	At day 30, confirmed recovery of platelets (per protocol)	30	Yes	0
3	At day x b (1 st measurement of platelet recovery), confirmed recovery of platelets, ideal case (per protocol)	x	Yes	0
4	No event occurred and subject is no longer in trial at day x b (including replaced subjects who are dosed)	x	No	1

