**Appendix II – Protocol ALX-0681-2.1/10: Definition of ‘Major’ Protocol Deviations (PDs) for Data Analysis**

Major PD categories	Remarks	Source	How to assess?	DVTERM	DVDECOD
Inclusion criteria					

If one inclusion criterion or more are not met subject may not be randomised;
 
 
18 years of age or older
 
Men or women willing to accept an acceptable contraceptive regimen
 
Subjects with clinical diagnosis of TTP
 
Necessitating PE
 
Subject accessible to follow-up
 
Obtained, signed and dated informed consent
 
	
For #6: IC has to be signed and dated by subject or legal representative before inclusion in the study
	
██████████ ██████████ ██████████ ██████████
	
Review of listings or edit checks
	
Inclusion criterion 1-6 not met
	
Eligibility criteria not met

Exclusion criteria					

If one or more exclusion criteria are met subject may not be randomised;
 
 
Platelet count greater or equal to 100,000/<math>\mu</math>L
 
Severe active infection indicated by sepsis (requirement for pressors with or without positive blood cultures)
 
Clinical evidence of enteric infection with E. coli 0157 or related organism
 
Anti-phospholipid syndrome
 
Diagnosis of disseminated intravascular coagulation (DIC)
 
Pregnancy or breast-feeding
 
Haematopoietic stem cell or bone marrow transplantation-associated thrombotic microangiopathy
 
Known congenital TTP
 
Active bleeding or high risk of bleeding
 
	
Essential laboratory assessments to be done and recorded in the CRF:
 
 
Local lab platelet count at screening/baseline (missing platelet count is major PD)
 
–
 
–
 
At least 1 anti-PL ab test at screening/baseline (no anti-PL result (anticardiolipin test) is major PD)
 
–
 
Neg. pregnancy test (urine or serum) (major PD if positive; minor PD
 
	
██████████
	
Review of listings or edit checks
	
Exclusion criterion 1-18 not met
	
Eligibility criteria not met

Major PD categories	Remarks	Source	How to assess?	DVTERM	DVDECOD

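### The Cox models in SAP 6.3.1 leave out baseline platelet count, the starting value of the primary endpoint; if it is prognostic, no planned analysis corrects the hazard ratio for it

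*SAP*

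**What the plan says.** The primary event (SAP Section 3 and 6.3.1) is the first platelet count of at least 150,000/µL within 30 days of first study drug. It must be confirmed 48 hours later by a fresh count at that level and an LDH of at most 2 × ULN. The test is a one-sided 2.5% log-rank test, and the Kaplan-Meier analysis is stratified by whether one PE session preceded randomisation.

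Two Cox analyses accompany it:

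- **Subgroup analyses.** The SAP uses "the corresponding Cox proportional hazard regression model with baseline disease characteristics" and names ADAMTS13 activity, vWF level, first or recurrent episode, RICO suppression during treatment, and prior PE.
- **Sensitivity item 2.** "Analysis of treatment effect adjusted for the following covariates" has the same five items. Besides treatment, "significant (5% significance level; SL) covariates are retained".

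Platelet count is in neither list, yet the value exists. Protocol 8.1.1 puts it in the screening haematology panel. SAP Appendix II requires it: "Local lab platelet count at screening/baseline (missing platelet count is major PD". SAP 6.2.4 tabulates it: "Baseline disease characteristics presented will be platelets, LDH, ADAMTS13 activity". Protocol 5.2 bounds it from above, because the first exclusion criterion is "Platelet count greater or equal to 100,000" per µL. Protocol 7.5 describes a computerised randomisation schedule and mentions no stratification by platelet count.

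**The concern.** The endpoint is a threshold on the same scale as the baseline measurement. A subject entering just under 100,000/µL needs a rise of a little over 50,000/µL; one entering near zero needs almost 150,000/µL. It is reasonable to ask whether the starting count predicts time to response.

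If it does, two things follow. First, in a Cox model an omitted prognostic covariate pulls the estimated treatment HR towards 1, even with perfect balance. Second, a chance difference in mean starting count between the arms shifts the unadjusted HR. The purpose of an adjusted sensitivity analysis is to show whether baseline differences explain the result. Without the starting value of the endpoint it cannot answer the first question a reader will ask, and adding that value after unblinding would look post hoc.

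**Working it through.** **Inputs from SAP 6.1.4.** Control median 6 days, ALX-0081 median 3.36 days, HR 6/3.36 = 1.786, one-sided α 2.5%, power 80%, 1:1 allocation, 15% lost to follow-up, 30-day window, N = 110.

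**Input not in the documents.** The prognostic strength of baseline platelets is an assumption: response HR per SD from 1.0 to 2.0.

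**Step 1: the plan's sample size.** Schoenfeld events = 4(z₀.₉₇₅ + z₀.₈₀)²/(ln HR)² = 4 × (1.960 + 0.842)²/(0.580)² = 93.4. Dividing by 0.85 gives 109.9, so 110 is reproduced. At 110 × 0.85 = 93.5 events the power is 80.0%.

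**Step 2: simulation.** 2,000 trials per row, 55 per arm, exponential times, control median 6 days, conditional HR 1.786, censoring at 30 days, and 15% of subjects lost uniformly over the 30 days. Baseline platelets are a standard normal covariate. Each trial was fitted by a Cox model with treatment only and with treatment plus platelets, tested at z > 1.96. The last column is the share of trials in which platelets would pass the SAP's 5% retention rule.

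| HR per SD | HR without | HR with | Power without | Power with | Platelets retained |
|---|---|---|---|---|---|
| 1.0 | 1.81 | 1.82 | 84% | 84% | 5% |
| 1.2 | 1.76 | 1.79 | 79% | 81% | 44% |
| 1.35 | 1.73 | 1.81 | 78% | 84% | 83% |
| 1.5 | 1.68 | 1.79 | 73% | 80% | 97% |
| 2.0 | 1.58 | 1.81 | 61% | 82% | 100% |

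Monte Carlo error on power is about 1 point. The first row exceeds 80% because lost subjects contribute time and events until they leave (about 105 events on average, against 93.5 in Step 1). That matches case 4 of SAP Table 1, which censors a subject on leaving.

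**Step 3: chance imbalance.** The SE of the difference in standardised means is √(2/55) = 0.191, so the 95% range is ±1.96 × 0.191 = ±0.37 SD. In the simulation the unadjusted log HR moved by 0.205, 0.385 and 0.521 per SD of imbalance at HR per SD 1.2, 1.5 and 2.0. The factor exp(slope × 0.374) is 1.080, 1.155 and 1.215, in either direction.

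**Step 4: type I error.** With no treatment effect, and HR per SD of 1.0, 1.5 or 2.0, rejection was 2.7% to 2.9% without and 2.5% to 3.0% with platelets. Both are nominal within simulation error.

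**Limits.** The simulation used an untruncated normal covariate and no prior-PE strata.

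**The case against.** The strongest reply is that nothing in the documents shows baseline platelets to be prognostic among subjects already below 100,000/µL. A shorter distance in counts need not mean a shorter time. At HR 1.2 per SD the cost is about 2 power points and a shift in HR from 1.79 to 1.76, which is close to nothing. This stands, and it is why the point is conditional.

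Second, the affected models are supportive. Success rests on the log-rank test, so adding a covariate to a Cox model recovers no primary power. The unadjusted HR is also not an error: it is a valid marginal estimate, smaller than the conditional one. Both statements stand. Stratifying by prior PE may absorb some of the same variation.

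Third, an imbalance would not go unseen. SAP 6.2.4 tabulates baseline platelets and LDH, and 6.1.1 has all data summarised by treatment group. That is right for the imbalance itself. It does not cover the consequence, because no planned analysis shows how far an imbalance moved the HR.

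Fourth, simply adding platelets to the existing list would not work. The retention rule could drop them, and the list contains RICO suppression throughout treatment, which is measured after dosing and reflects the drug's action. In Protocol Table 6 RICO fell below 20% in 15 of 15 subjects given 10 mg (3 + 6 + 6) and in 0 of 9 given placebo (5 + 2 + 2). An HR adjusted for it would remove much of the effect being estimated. This stands and shapes the fix.

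**Conclusion.** The omission is plain in the text, and the covariate is collected, cheap to use and on the endpoint's own scale. The size of the consequence is unknown: nil with no association, about 2 power points at HR 1.2 per SD, about 7 at 1.5 and about 21 at 2.0. The corresponding unadjusted HRs are 1.76, 1.68 and 1.58 for a conditional 1.786. This is a worthwhile improvement to a supportive analysis, not a flaw in the primary one.

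A reader might infer more than the documents support:

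- **That the treatment effect is diluted in this trial.** This needs a prognostic strength that the documents do not give.
- **That the trial is underpowered at 61% or 73%.** Those figures rest on that assumption and on reading 1.786 as the effect at a fixed starting count. The SAP derives 1.786 from two group medians, so it can equally be read as the marginal effect, which is what an unadjusted analysis estimates.
- **That the primary test is invalid.** Type I error is nominal either way.
- **That baseline LDH must be added too.** It is part of the confirmation criterion, but no calculation here supports a size for its effect.

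**What to change.** Keep the stratified log-rank test primary. In SAP 6.3.1, before database lock:

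1. Pre-specify one supportive Cox model with treatment, prior PE and baseline platelet count (continuous or log-transformed, the form chosen in advance). Report its HR and 95% CI next to the primary result.
2. Force platelet count into the model and exempt it from the 5% retention rule.
3. Restrict this model to covariates measured before study drug starts. RICO suppression throughout treatment does not belong in it.
4. State how a missing baseline count is handled. SAP 6.1.2 lets a screening value stand in only if there was no PE before randomisation. After a prior PE the gap stays open, and the subject would drop out of the model although still in the ITT population.

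Baseline LDH as a multiple of ULN is optional. The cost is a short SAP addition and one degree of freedom (two with LDH) against roughly 93 planned events. If platelets turn out not to be prognostic, almost nothing is lost: power is 84% with or without them.

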## 6.1 Statistical and Analytical Issues

### 6.1.1 Statistical Methods

All data will be summarised by treatment group. In addition, where appropriate, a total overall group column will be included to summarise all subjects. Where appropriate, data will be summarised by treatment group and visit or whenever the assessment is done (e.g. the 1 and 3 week post-last day PE sampling may be done at the weekly visit, even if not at exactly 1 or 3 weeks).

All data will be listed and some selected variables will be tabulated or presented graphically, and will be noted where appropriate.

In summary and analysis tables of continuous variables, the minimum and maximum statistics will be presented to the same number of decimal places as the original data. The mean, median, quartiles, Least Squares mean (LS mean), and 95% Confidence Interval (CI) will be presented to one more decimal place than the original data, the standard deviation (SD) and standard error (SE) will be presented to two more decimal places than the original data. Standard descriptive statistics (number of subjects with data available [n], mean, SD, median, minimum and maximum) will be presented in summary tables. The LS mean, SE and 95% CI will be presented in the statistical analysis outputs as appropriate.

In summary tables of categorical variables, the number of non-missing observations and percentages will be presented. The denominator for each percentage will be the number of subjects within the population of interest [N] (unless otherwise specified).

All hypothesis testing will be 2-sided unless otherwise specified and carried out at the 5% significance level and designed to evaluate the superiority of ALX-0081 to placebo.

P-values will be rounded to three decimal places. P-values less than 0.001 will be reported as <0.001. P-values greater than 0.999 will be reported as >0.999.

Should any of the statistical methods (other than the primary endpoint analysis) proposed prove unsuitable during the final analysis, more appropriate methods will be used, and any changes documented in the CSR, including the rationale for use.

All statistical analysis will be performed using SAS® v9.2 or higher.

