### 6.1.4 Determination of Sample Size

The primary endpoint of time-to-response of blood markers (defined as time-to-response) is monitored in a survival setting. The time-to-response of blood markers comprises recovery of platelets  $\geq 150,000/\mu\text{L}$ . Accrual period was taken as 1.5 years. Actual accrual time is longer than 1.5 years; however there is no impact on the sample size. Zero to time to event period is set at 30 days. As median time-to-response for the control group we take 6 days (this information is calculated based upon Bandarenko *et al.*). For the treated group with ALX-0081 we assume a 44% risk reduction corresponding to a reduction in median time to event of 2.64 days, and ultimately resulting in a time-to-response of 3.36 days. The hazard ratio is defined in the SAS code as the ratio of control versus experimental (ALX-0081) treatment thus equaling to  $6/3.36=1.786$ . The sample size calculations are performed based on a log-rank test, aiming for a power of 80%, tested 1-sided at 2.5% significance level with 1:1 randomisation. Note that we assume that 15% of subjects would be lost-to-follow-up. The latter is justifiable because the active follow-up period (time of first study drug administration to time to event) only

---

equals 30 days. Based on the above described assumptions a sample size of 110 adult subjects is required. As subjects can be replaced, the ITT population may be larger than 110 subjects.

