## 6.3 Efficacy Analysis

### 6.3.1 Primary Efficacy Variable

#### *Primary endpoint*

Time-to-response, as defined in [Section 3](#), based on the following criteria:

- Recovery of platelets  $\geq 150,000/\mu\text{L}$
- This response must be confirmed at 48 hours after the initial reporting of platelet recovery equal to or above  $150,000/\mu\text{L}$  by a *de novo* measure of platelets  $\geq 150,000/\mu\text{L}$  and  $\text{LDH} \leq 2 \times \text{ULN}$  (*i.e.* “confirmed platelet response”)

Time-to-response will be measured in days, hours and minutes from date of first study drug administration. A Kaplan-Meier (KM) analysis with time-to-response as the end point and treatment group as the independent variable and stratified for absence/presence of one PE session prior to randomisation will be performed on the ITT and PP populations. An observation is censored if the observation does not meet the defined time interval of 30 days after first administration of study medication, due to any cause of loss-to follow-up (including death), or endpoint not being reached. The resulting survival estimates will be presented graphically. The median, 25th and 75th percentile time-to-event data will be presented in a table with 95% CIs (if they exist). ALX-0081 will be compared to placebo using a one-sided log-rank test in order to assess superiority at 2.5% significance level. The log-rank test is one-sided because a reduction in time-to-response by ALX-0081 is expected compared to placebo due to an inhibition of vWF by ALX-0081 (based on pre-clinical data).

---

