### *Censoring and event plan*

The primary endpoint in this trial is time to (initial) response. The event or response is defined as confirmed recovery of platelets above or equal to  $150,000/\mu\text{L}$ .

- Confirmed response means that 48 hours after the initial response, platelets remain above or equal to this cut-off (*de novo* measurement), and lactate dehydrogenase (LDH)  $\leq 2 \times$  upper limit of normal (ULN).
- ‘Time to’ is defined as time in days, hours and minutes between the event and the first administration of study drug. The initial time of reaching platelets above or equal to 150,000/ $\mu$ L is considered as the time of recovery of platelets, and must occur within 30 days after first administration of study drug. However, this initial recovery of platelets must be confirmed at 48 hours after initial reporting, implying that time of confirmation may be 48 hours later than 30 days after first administration.

Assessment of the primary endpoint is performed by using a one-sided log-rank test at 2.5% significance level. A Kaplan-Meier (KM) analysis with time-to-response as the endpoint and treatment group as the independent variable, and stratified for absence/presence of one PE session prior to randomisation, will be performed on the ITT population (all randomised subjects).

An observation is censored if the observation does not meet the defined time interval of 30 days after first administration of study drug medication, due to any cause of loss to follow-up (including death), or endpoint not being reached within the defined time interval. Only right censoring is applicable to this trial. In **Table 1**, different potential response (censoring/event) scenarios are presented.

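### The adjusted Cox sensitivity analysis keeps covariates only if significant at 5%, so listed prognostic factors, including prior plasma exchange, can be dropped by chance

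*SAP*

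**What the plan says.** SAP 6.3.1, sensitivity analyses, item 2, lists five covariates for an adjusted analysis of the treatment effect: (a) baseline ADAMTS13 activity, below 5% or not; (b) vWF level, continuous; (c) first or recurrent episode; (d) RICO suppression throughout treatment; and (e) "absence/presence of one PE session prior to randomisation". A Cox model is then fitted in which "in addition to treatment, significant (5% significance level; SL) covariates are retained".

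The item does not say whether selection is backward, forward or in one step, nor whether covariates are tested singly or jointly. It gives no sidedness for the retention test, so the default in SAP 6.1.1 applies: "All hypothesis testing will be 2-sided unless otherwise specified and carried out at the 5% significance level".

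The primary Kaplan-Meier analysis in the same section is "stratified for absence/presence of one PE session prior to randomisation", and the censoring and event plan repeats this. No selection is involved there.

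A further Cox model appears under Subgroup analyses in SAP 6.3.1: "In addition to the KM estimates, the corresponding Cox proportional hazard regression model with baseline disease characteristics". It names the same five variables and reports an HR with a 95% CI. It states no retention rule.

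**The concern.** The five covariates in item 2 are only candidates. Which of them stand behind the adjusted treatment HR is decided by the trial data, at a threshold that has little power for moderate effects in a trial of this size. Prior PE is one of the candidates. If it fails the screen, the sensitivity analysis no longer accounts for the factor that the primary Kaplan-Meier analysis accounts for, and the two results are harder to compare. The reported confidence interval would also treat the selected model as though it had been fixed in advance.

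**Working it through.** **1. The plan's own figure.** Inputs from SAP 6.1.4: medians of 6 and 3.36 days, HR 6/3.36 = 1.786, 80% power, "tested 1-sided at 2.5% significance level with 1:1 randomisation", 15% loss to follow-up. By Schoenfeld's formula, events = 4 × (1.960 + 0.842)² / (ln 1.786)² = 93.4, or 94. Then 93.4/0.85 = 109.9, which reproduces 110.

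**2. Expected events with 110 subjects.** With exponential times, the 30-day response is 1 − 2^(−30/6) = 0.969 on control and 1 − 2^(−30/3.36) = 0.998 on ALX-0081, average 0.983. Events = 110 × 0.85 × 0.983 = 92. I use 92 to 94.

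**3. Chance that a real binary covariate is kept.** SE(log HR) = 1/√(d·p(1−p)), with d events and prevalence p. The chance of retention is P(|Z| > 1.96) with Z centred at log HR/SE. Example: d = 92, p = 0.20, HR 1.5 gives 0.405 × √14.72 = 1.556, hence 34%.

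The covariate HRs and prevalences below are assumptions. Protocol 4.2 describes prior PE only as exceptional and gives no share. Each cell shows 92 / 94 events.

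| True covariate HR | p = 10% | p = 20% | p = 50% |
|---|---|---|---|
| 1.5 | 21% / 22% | 34% / 35% | 49% / 50% |
| 1.786 (size of the assumed drug effect) | 39% / 39% | 60% / 61% | 79% / 80% |
| 2.0 | 51% / 52% | 76% / 77% | 91% / 92% |

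For an 80% chance of retention with 94 events, the true HR must be about 2.62 at 10% prevalence, or 1.78 at 50%. The formula does not apply to vWF level, which is continuous. In the other direction, five independent null covariates would leave at least one in the model with probability 1 − 0.95⁵ = 22.6%.

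A simulation (110 subjects, 15% loss, 30-day cut-off, one covariate, 2,000 runs per setting) agrees. HR 1.5 was dropped about 74%, 54% and 49% of the time at 10%, 30% and 50% prevalence.

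**4. What this does to the treatment HR (true value 1.786).**
- One covariate (HR 1.5 to 2.0, prevalence 10% to 50%): mean treatment HR 1.81–1.82 with the covariate forced in, 1.80–1.81 under 5% selection, 1.72–1.80 if always omitted. Power was 79–82% forced in and 79–82% selected. One-sided type I error was 2.4–3.6% forced in and 2.6–3.8% selected.
- Several prognostic covariates with backward elimination (my choice of procedure, on assumed effects): mean HR 1.84 forced in and 1.82 selected, a difference of 0.02/1.84 = 1%. Coverage of the 95% CI was 93.5% and 92.6%; power was 78.9% and 77.9%.
- In individual trials of that second simulation the two HRs differed by up to about 11% (95th percentile). They disagreed on significance about 4% of the time.

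**The case against.** The strongest reply is that the treatment HR barely moves. Selection keeps strong factors and loses mainly weak ones, and step 4 bears this out on average. That stands, and it rules out several stronger readings.

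- A reader might infer that dropped covariates pull the treatment HR materially towards 1. That attenuation belongs to a model that always omits the covariate, which is not what the SAP plans.
- A reader might infer that real prognostic factors will be dropped. They can be; how often depends on effects and prevalences that the documents do not give.
- A reader might call the analysis irreproducible. The candidate list, the forced treatment term and the 5% level are all written down. The gap is narrower: the selection procedure is not named, so two analysts could reach different models.
- A reader might infer that the primary result is at risk. The rule touches a sensitivity analysis only. The stratification wording is attached to the Kaplan-Meier analysis, and the log-rank test is not itself described as stratified.

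It can also be said that the Cox model under Subgroup analyses already supplies an unselected fit. That is only partly so. The paragraph goes on to discuss treatment-by-subset interactions and never says that it is the fixed counterpart of item 2. It leaves two Cox specifications unreconciled.

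Finally, forcing covariates in may lose subjects. Protocol Table 10 schedules pre-dose ADAMTS13 at screening only, and SAP 6.1.2 does not let screening values replace missing baseline values in subjects with prior PE. The baseline definition in SAP section 3 (last assessment before first dose) may resolve this, but the text does not say so. The fix has to deal with it.

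**Conclusion.** The concern holds as a low-severity point about pre-specification. The adjusted estimate will come from a data-dependent model that may omit prior PE and so fail to match the primary Kaplan-Meier analysis. With 92 to 94 events, a binary factor of true HR 1.5 and prevalence 50% or less is lost about half the time or more. The average cost is about 1% in the treatment HR and about 1 percentage point in power and coverage. In a single trial, though, the choice of model can shift the estimate noticeably. These sizes rest on assumed covariate effects and prevalences and on exponential response times. Nothing here alters the primary test, its significance level or the sample size of 110.

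**What to change.** Replace the retention rule in item 2 with one fixed Cox model: treatment, baseline ADAMTS13 activity (below 5% versus 5% or more), baseline vWF level, and first versus recurrent episode, stratified by prior PE. Remove nothing on significance. Report the treatment HR with its 95% CI.

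In the same edit:
- State that the pre-dose (screening) ADAMTS13 value counts as baseline, so that subjects with prior PE are not lost as incomplete cases.
- Leave out RICO suppression throughout treatment. It is measured after randomisation and is affected by the drug.
- Say how this model relates to the Cox model under Subgroup analyses, or merge the two.

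The cost is SAP wording. The model carries three covariate parameters besides treatment, which about 92 events support, and any subject with a missing covariate would drop out of this analysis.
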